**Anti-helminthic treatment:** Children >1 year of age will be given mebendazole, 100 mg two times daily for 3 days, if such treatment has not been provided in the last six months. This treatment will be provided after two weeks of nutritional rehabilitation.

**Follow-up:** After the child is discharged from the NRU, a health worker will visit the child every week for one month and then at fortnightly intervals until the child achieves an oedema-free WH >80%. During each visit, the child's general condition will be assessed, weight and height (or length) measured, presence or absence of oedema noted, supplies of micronutrients provided, compliance of feeding and micronutrient supplementation checked by 24 hours recall, and morbidity recorded, if any. To aid recall of morbid conditions, on each visit mothers will be given a pictorial calendar portraying a well child and children with diarrhoea, vomiting, cough, fever, eye infection, or discharging ears [10]. Mothers will be requested to record daily on the calendar whether the condition had been present or absent in the previous 24 hours. Morbidity will then be recorded on a precoded form with the help of the calendar. Diarrhoea will be defined as the passage of three or more watery or liquid stools per day. An episode will be considered new if at least two diarrhoea-free days intervene between the present and previous episodes. The health worker's identification of children with pneumonia of different grades of severity will be based upon WHO guidelines [11]. Lack of weight gain for two consecutive visits will constitute failure to respond. The health worker will refer to the CRSC any child with suspected serious illness, i.e., diarrhoea with some or severe dehydration, pneumonia, ear or throat infection, repeated episodes of fever, loss of appetite, or failure to respond to feeding. Self referral will also be encouraged and entertained at any hour of the day. The child will be evaluated and managed accordingly by any of the investigators (during day time) or the on-duty physician (at night). Readmission to the hospital and the NRU will depend upon existing CRSC guidelines. Any child readmitted to the NRU will not be re-enrolled into the study, but will maintain the pre-readmission status as a study subject. The physician will also record in the precoded form diagnosis, treatment, duration, and outcome of any severe illness including relapse of severe malnutrition or septicemia.

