### **Sample Size**

A preliminary analysis of 51 severely malnourished children (WH <70%) who received nutritional rehabilitation in our NRU after recovering from diarrhoea showed that the weight gain was  $8.4 \pm 7.3$  g/kg.day, and the time to achieve WH >80% was  $22.5 \pm 6.2$  days. In designing a trial with three or more groups, it is suggested that pair-wise comparisons between groups of central interest be first decided upon [13]. It is assumed that the proposed method of home-based nutritional rehabilitation with outpatient follow-up will result in a relatively lesser weight gain of 4 g/kg per day, will require approximately 35 days to achieve WH >80%, and lead to a 35% reduction in cost of treatment. Sample sizes of 58, 15, and 24 children in each group (hospital and home-based) were calculated from the assumptions of weight gain, time to achieve WH >80%, and reduction in cost of treatment respectively.

The formula used for calculating sample size is:

$$\frac{2 (SD)^2}{WD^2} \times \text{factor for } \alpha, \beta$$

where, SD is the standard deviation, WD is the worthwhile difference, power of detection is 90%, and type I error is 0.05. Taking the greatest of the three calculated sample sizes and allowing for 20% dropouts (refusal to continue, unexpected migration of the family to an outlying area, or later diagnosed to have tuberculosis), a sample size of 75 children in each group has been estimated.

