### **Outcome Measures**

- Time to recovery (achievement of WH 80%, oedema-free), in days
- Rate of weight gain, in g/kg per day calculated from lowest weight to discharge weight
- Speed of loss of oedema, in days
- Failure to respond
- Morbidity, in number and duration of episodes over equal periods of follow-up for both groups
- Mortality
- Cost of treatment

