## Data Analysis

Describe plans for data analysis. Indicate whether data will be analyzed by the investigators themselves or by other professionals. Specify what statistical softwares packages will be used and if the study is blinded, when the code will be opened. For clinical trials, indicate if interim data analysis will be required to monitor further progress of the study. (TYPE WITHIN THE PROVIDED SPACE).

Data will be analyzed using the SPSS Windows software. The Epi Info software will be used to calculate anthropometric indices. Enrollment characteristics will be compared between the three treatment groups. The outcome variables will be compared both within and between groups from enrollment to discharge. For normally distributed quantitative variables, means will be compared by ANOVA. Variables not normally distributed will be log transformed before analysis. Categorical variables will be compared by Chi-square test, multiple or logistic regression will be performed to minimise bias if required.

Results from all randomized children will be included in the analysis of the study. Data from children withdrawn because of failure to respond, TB, or voluntary dropout will be included in the analysis upto the time of withdrawal. A supplementary analysis excluding the children withdrawn may also be made.

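### Time to recovery falls under ANOVA of means, which has no valid place for a child withdrawn or dead before recovering

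*Protocol*

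**What the plan says.** The protocol's Outcome Measures section lists first "Time to recovery (achievement of WH 80%, oedema-free), in days". Speed of loss of oedema, also in days, is another outcome. Failure to respond and mortality are listed separately.

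Data Analysis gives one rule for quantitative outcomes: "For normally distributed quantitative variables, means will be compared by ANOVA". If they are not normal, "Variables not normally distributed will be log transformed before analysis". The only other methods named are the chi-square test and multiple or logistic regression. None of these handles a time cut short before the event.

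On who is analysed, the same section says "Results from all randomized children will be included in the analysis of the study". It adds "Data from children withdrawn because of failure to respond, TB, or voluntary dropout will be included in the analysis upto the time of withdrawal", and then "A supplementary analysis excluding the children withdrawn may also be made".

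The Follow-up paragraph under Treatment A defines failure to respond as no weight gain at two visits in a row and has such children referred to the hospital. It says "Any child readmitted to the NRU will not be re-enrolled into the study, but will maintain the pre-readmission status as a study subject". Home visits run until recovery, with no last day set. The Sample Size section plans for unobserved endpoints, "allowing for 20% dropouts", and describes these as refusal, migration or a later diagnosis of tuberculosis.

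**The concern.** Recovery time exists only for a child who recovers. For a child who leaves the study or dies first, an analysis of mean days, raw or logged, has two options. It can leave the child out, which does not fit the promise to analyse every randomized child. Or it can enter the days to withdrawal, which counts an unrecovered child as recovered early. A log transform deals with skewness and does nothing for incomplete times.

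The choice matters because failure to respond is one of the named reasons for withdrawal. A child who is not gaining weight is not approaching the weight-for-height target, so at least part of the withdrawal is tied to the outcome. The first hypothesis is that these children can be managed at home, and the children who are slow or never recover carry much of the evidence on it. The optional analysis without withdrawn children cannot serve as a check, since it is the omission option itself.

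**Working it through.** **Inputs from the Sample Size section.** Hospital time to the target is 22.5 days, SD 6.2. Home care with outpatient follow-up is expected to take about 35 days. The difference is 35 − 22.5 = 12.5 days.

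**The plan's own figure.** The weight-gain size reproduces: 2 × 7.3² / 4.4² × 10.5 = 57.8, so 58 per group. Weight gain therefore sets the sample size. No printed figure depends on how unrecovered children are handled, so what follows is an illustration and corrects no stated number.

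**Assumptions, not in the documents.** Recovery times are normal. The home SD is either 6.2 (as in hospital) or 6.2 × 35 / 22.5 = 9.6 (same relative spread). The withdrawal day W is uniform on days 7 to 35. A share d of each arm is due to be withdrawn; those who recover before day W count as recovered.

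**1. Withdrawal day used as the time.** The arm mean is (1 − d) × E[T] + d × E[min(T, W)], where E[min(T, W)] is the integral of P(T > x) × P(W > x). By simulation this is 20.2 days in B with SD 9.6, 20.7 with SD 6.2, and 17.5 in C.

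| Withdrawn B / C | Home SD | Mean B | Mean C | Difference |
|---|---|---|---|---|
| 20% / 20% | 9.6 | 0.8×35 + 0.2×20.2 = 32.0 | 0.8×22.5 + 0.2×17.5 = 21.5 | 10.5 |
| 20% / 20% | 6.2 | 0.8×35 + 0.2×20.7 = 32.1 | 21.5 | 10.6 |
| 30% / 10% | 9.6 | 0.7×35 + 0.3×20.2 = 30.6 | 0.9×22.5 + 0.1×17.5 = 22.0 | 8.6 |
| 30% / 10% | 6.2 | 0.7×35 + 0.3×20.7 = 30.7 | 22.0 | 8.7 |
| 10% / 30% | 9.6 | 0.9×35 + 0.1×20.2 = 33.5 | 0.7×22.5 + 0.3×17.5 = 21.0 | 12.5 |

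The last row shows that the errors in the two arms can cancel. The size of the bias in the difference depends on who leaves and when.

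**2. Omission, withdrawal unrelated to recovery.** Under the same assumptions the difference among the remaining children is 12.4 to 12.6 days at 20% / 20% and 12.0 to 12.4 at 30% / 10%. The bias is small.

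**3. Omission, the slowest children withdrawn.** The mean of the fastest fraction p of a normal distribution is μ − σ × φ(z_p) / p.

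- Slowest 20% omitted: φ(0.842) / 0.80 = 0.280 / 0.80 = 0.350. The home mean is 35 − 9.6 × 0.350 = 31.6, or 35 − 6.2 × 0.350 = 32.8.
- Slowest 15% omitted: 0.233 / 0.85 = 0.274. The home mean is 32.4 or 33.3.

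With C unaffected at 22.5, the difference reads between 31.6 − 22.5 = 9.1 and 33.3 − 22.5 = 10.8 days.

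**4. Simple censoring of failures.** With home SD 6.2 and 20% withdrawn on days 7 to 28, the Kaplan-Meier median is 35.0 if withdrawal is unrelated to recovery, but 33.5 if the slowest 20% are withdrawn and censored. Changing to survival curves is therefore not enough; failures must not be censored when they leave.

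**The case against.** Several things can fairly be said for the plan.

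- **The method is not assigned by name.** Data Analysis never says that ANOVA applies to time to recovery. Including data up to withdrawal suits weight, morbidity and cost, and could loosely describe censoring. A reader might infer that the plan orders the withdrawal day to be entered as the recovery day; no sentence says so. What remains is that the outcome is quantitative, in days, and the text offers no other method for it. A separate analysis plan may exist, but the protocol's own rule does not suit this outcome.
- **Omission is not always biased.** This stands: if leaving is unrelated to recovery, it costs about half a day at most in these runs.
- **The withdrawal patterns are assumed.** This stands too. A reader might take the 20% in the Sample Size section as a failure rate, but it covers refusal, migration and tuberculosis.
- **The two sections need not conflict.** A reader might see a contradiction between Treatment A, which keeps a readmitted child as a study subject, and Data Analysis, which lists failure as a reason for withdrawal. A failing child could be readmitted and retained, or withdrawn, so both can be true. The gap is that nothing says which applies when.
- **Failures are visible elsewhere.** Failure and mortality are separate outcomes, defaulters in treatment B are traced at home, follow-up runs until recovery, and no primary outcome is designated. This limits the harm but does not repair the comparison of times.

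**Conclusion.** The point holds. The only method the protocol names for quantitative outcomes cannot validly analyse time to recovery, or time to oedema loss, once any child leaves or dies before the event.

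If the withdrawal day is used, a true 12.5-day difference reads about 10.6 days with equal 20% withdrawal, and about 8.6 with 30% in B and 10% in C. If children are omitted, the error is negligible when withdrawal is unrelated to recovery. If the slowest 15-20% of home children are lost, their mean drops from 35 to about 32-33 days. These sizes rest on the assumed home SD, withdrawal days and withdrawal shares; the documents give no rate of withdrawal for failure.

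The documents do not support the stronger conclusion that the results will favour home care. They do not show which arm will have more or earlier withdrawals, and with the opposite split the illustration shows almost no net error.

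**What to change.** For time to recovery and time to oedema loss, replace ANOVA with a time-to-event comparison from randomization to a common last day: Kaplan-Meier or cumulative incidence curves, with a log-rank or Cox test.

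- Censor children withdrawn for tuberculosis, and voluntary dropouts, at last contact.
- Treat death as a competing event.
- Count children who fail to respond as not recovered through the common last day unless recovery is recorded. Do not censor them at withdrawal.
- Report the proportion recovered by that day in each arm.

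The common last day has to be set in advance; the documents give none, and it should lie well beyond the 35 days expected at home. The Follow-up text under Treatment A and the Data Analysis section must be reconciled on whether a child who fails to respond remains a study subject. None of this asks for a change in clinical management. It asks that outcomes go on being recorded after withdrawal where parents agree.

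The cost is more than a change of wording: some extra outcome recording after withdrawal, and slightly more analysis work. Withdrawn children are to receive conventional treatment at the same centre (Ethical Assurance section), which should make that recording feasible for many of them.

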## Clinical Economics

A complete, cost-benefit analysis from institutional as well as societal perspectives will be performed for all groups, starting from 7 days after randomization (point at which differential costs start). Cost of treatment to the CRSC will include capital and administrative costs, and expenses incurred for food, medicines, and laboratory tests. The cost of treatment to the parents will include expenses incurred for food, wage loss, transport and help needed at home during the mother's absence. This will be done in collaboration with the Health Economics Programme of ICDDR,B.

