Upon resolution of acute illnesses including diarrhoea, pneumonia, gross electrolyte imbalance, or septicemia, severely malnourished children aged 6 months to 5 years will be randomized to receive any of the three treatment regimens:

1. Home-based nutritional rehabilitation with home follow-up (treatment A, n=75)
2. Home-based nutritional rehabilitation with outpatient follow-up (treatment B, n=75)
3. Hospital-based nutritional rehabilitation (treatment C, n=75).

Children on treatments A and B will stay in the NRU of the CRSC for a period of 7 days, during which their condition will stabilise and their mothers will have learnt the preparation of *khichuri* and *halwa*, which are low-cost, nutritious diets being successfully used in the CRSC. Following discharge after 7 days, these children will continue to be fed *khichuri* and *halwa* prepared by the mothers at home. Children on treatment A will be visited at home for follow-up by health workers at regular intervals during which growth will be monitored, micronutrients supplied, and morbidity recorded. This will continue until the children achieve an oedema-free weight-for-height (WH) >80%. Children on treatment B will be required to attend the outpatient follow-up clinic until they achieve oedema-free WH >80%. Children on treatment C will remain in the NRU and fed *khichuri* and *halwa* according to a standardized dietary schedule until achievement of a WH >80%. Outcome measures that will be used in comparing the three treatments will include growth, time to recovery (achievement of oedema-free WH >80%), rate of weight gain in g/kg per day calculated from lowest weight to discharge weight, speed of loss of oedema, failure to respond, morbidity (number and duration of episodes over equal periods of follow-up for both groups), mortality, and cost of treatment.

KEY PERSONNEL (List names of all investigators including PI and their respective specialties)

Name	Professional Discipline/Specialty	Role in the project
1. [name]	Paediatrician & Nutritionist	P.I.
2. [name]	Internist	Co-investigator
3. [name]	Paediatric Gastroenterologist & Nutritionist	Co-investigator
4. Medical Officer (to be named)	Physician	Co-investigator
5. [name] *	Nutritionist	Collaborating investigator

\* Reader in Community Nutrition  
London School of Hygiene & Tropical Medicine

Principal and co-investigators are from the Clinical Sciences Division, ICDDR,B.

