children, and the ingredients are locally available. *Khichuri* and *halwa* (appendix 1) are examples of such diets developed for severely malnourished children at the ICDDR,B with optimum amount of ingredients, and are being used successfully in nutritional rehabilitation [6]. *Khichuri* is an energy-dense diet prepared from rice, soya oil, vegetables, and lentils while *halwa* is a more energy-dense sweet diet made from rice flour, soya oil, lentils, and molasses. Both the diets provide energy as well as protein from vegetable sources that are inexpensive and easily available.

The Clinical Research and Service Centre (CRSC) of the ICDDR,B (popularly known as the "Cholera hospital") currently treats around 115,000 patients each year and about 60% of them are under-5 children. Nearly 80% of all children (about 5,500 children) requiring treatment in the inpatient units for a longer period of time (median period of stay, 4.5 days) suffer from severe malnutrition. After recovering from diarrhoea and associated medical problems, a few of them (due to bed constraints and refusal of mothers to stay in the hospital for a longer period of time) undergo nutritional rehabilitation in the NRU run by the Child Health Programme of the CRSC. The NRU has only 16 beds where the very severely malnourished children are admitted with their mothers, treated for a period of 15-30 days, and discharged when their WH exceeds 80%, they are free of oedema, and have a good general condition. The number of beds in the NRU is clearly far less than what is required. On the other hand, a large number of mothers refuse to stay in the NRU for a long period of time because of family commitments at home. A survey done in January-May 1998 revealed that among 340 severely malnourished children eligible for admission to the NRU of the CRSC, mothers of only 142 children (42%) agreed to have their children admitted to the NRU. Children who cannot be accommodated in the NRU or those who refuse to stay for a prolonged period of time in the NRU are advised to come for follow-up at regular intervals. However, the follow-up rates have always been sub-optimal.

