## Rationale

- If the hospital to home-based nutritional programme is found to be more cost-effective than the hospital-based programme, then it will be possible to rehabilitate more severely malnourished children with the same amount of available resources.
- It will be possible to extend the programme, if found to be effective, to other locations/health centres on a country-wide basis through governmental and non-governmental health care services.
- Home visits will provide health and nutrition education to the study mothers as well as neighbouring mothers, will help in the identification of medical problems and early referral of sick children to appropriate health centres.
- Active participation will help in confidence building of mothers on home management of severely malnourished children. Preparation and use of low-cost diets will help in preventing malnutrition among siblings as well as in subsequent children.

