## Patient Management

### Management of Acute Illness

As the children will be acutely ill with diarrhoea and other complicating illnesses including pneumonia, electrolyte imbalance, or septicemia, they will be treated in the inpatient units according to the standardized management protocol now being used in the CRSC. Implementation of this protocol resulted in a 47% reduction in mortality during the acute phase of treatment of severely malnourished children with diarrhoea admitted to the CRSC [9]. Duration of, and management provided during the acute phase of treatment will be recorded. Upon resolution of the acute illness, children will be randomized to receive any of the three interventions for nutritional rehabilitation and transferred to the NRU.

Criteria of resolution of acute illnesses are:

- Diarrhoea: No watery or liquid stools during the last 24 hours, no signs of dehydration, absence of blood or excessive mucus in stools.
- Pneumonia: No fast breathing (respiratory rate  $\leq 50$ /min in a child  $< 1$  year,  $\leq 40$ /min for a child  $\geq 1$  year of age), no chest indrawing, no wheeze, no cyanosis, able to drink, reduction in crepitations compared to admission auscultation.
- Electrolyte imbalance: Absence of lethargy or head lag, no irritability or fast breathing.

Septicemia: No signs of circulatory collapse (cold hands and feet, weak radial pulse, not alert), conscious, normal body temperature.

In addition, a child should be hungry and should not require a nasogastric tube for feeding.

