### **Treatment C**

Children on treatment C will remain admitted in the NRU until they have achieved an oedema-free WH >80%, and have a good general condition. This will typically involve a stay in the NRU for 15-25 days. The standardized feeding schedule will be followed and micronutrient supplements provided until discharge (refer to treatment A). Training of mothers or caretakers, immunization, and anti-helminthic therapy will be the same as in treatment A, except that in this treatment schedule the mothers or caretakers will receive more educational lessons due to their longer stay in the NRU. Morbid conditions occurring during rehabilitation, including diarrhoea, pneumonia, or septicemia will be recorded in precoded forms. After being discharged from the NRU, the children in this group will be advised to attend the NFU at intervals of two weeks for one month, and then at monthly intervals until they achieve a WH >90%. The entire family will be encouraged to come for the follow-up visit during which preparation of khichuri and halwa will be demonstrated to the mothers and then served to all members. Health education of the mothers or caretakers will be reinforced. Iron supplementation will be continued for 2 months in usual doses. Intercurrent illnesses such as diarrhoea or pneumonia will be treated.

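### Costing from day 7 leaves out the NRU week that every arm needs, so relative cost figures built on it would favour home care, although the absolute difference between arms is unaffected

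*Protocol*

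**What the plan says.** Clinical Economics promises a complete cost-benefit analysis, institutional and societal, for all groups, "starting from 7 days after randomization (point at which differential costs start".

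What falls in the uncounted week is clear from other sections. Under Management of Acute Illness, "children will be randomized to receive any of the three interventions for nutritional rehabilitation and transferred to the NRU", so day 0 is entry to the NRU. The Project Summary states that "Children on treatments A and B will stay in the NRU of the CRSC for a period of 7 days". Treatment C children simply remain there: "This will typically involve a stay in the NRU for 15-25 days". The Background gives routine NRU practice as "treated for a period of 15-30 days".

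The cost questions appear in four places:

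- Sample Size assumes that home-based care with outpatient follow-up will "lead to a 35% reduction in cost of treatment", with no period given.
- Hypothesis 2 compares the cost-benefit of the home and hospital programmes.
- The Rationale says that if home care proves more cost-effective, "then it will be possible to rehabilitate more severely malnourished children with the same amount of available resources". Item 7 of the abstract for the ethics committee repeats this.
- Outcome Measures lists cost of treatment, and Data Analysis compares outcome variables over a span that begins at enrolment, not at day 7.

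**The concern.** A cost common to all arms cancels in a difference but not in a ratio. Removing the first NRU week shrinks the denominator of any percentage saving or benefit-cost ratio, and it shrinks the home programme's own cost proportionally more than the hospital's. In planned NRU days, home care uses 7 against 22.5 over the whole course. Counted from day 7, it uses 0 against 15.5.

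The windows also disagree within the protocol. Cost is a listed outcome, and outcomes are compared from enrolment, yet the costing starts a week later. Time to recovery and weight gain include the first week, so a cost per recovered child would set a truncated cost against an untruncated outcome. Data Analysis also log-transforms non-normal variables. If costs are skewed and handled that way, the test compares ratios, and the omitted week does not cancel there either.

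At stake is how far the result supports extending the programme country-wide. A manager planning from day-7 ratios would expect more children per budget than a programme with a required NRU week can treat.

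**Working it through.** **The plan's own figures.** The sample size formula, with 90% power and two-sided 5%, has a factor of about 10.5. For weight gain, 2 × 7.3² / 4.4² × 10.5 = 57.8, so 58 per group, as stated. The 24 per group for the 35% cost reduction cannot be reproduced because no cost SD is given. Solving backwards, SD = √(24 × 0.35² / (2 × 10.507)) = 0.374, so 24 implies an SD of about 37% of the hospital mean. Nothing there shows which period the 35% covers.

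**Inputs.** Hospital stay L = 22.5 days (Sample Size, mean time to reach 80% weight-for-height, taken as counted from NRU entry), with 15 to 25 days under Treatment C and 15 to 30 days in the Background. The uncounted period is 7 days. Cost per NRU day is not given. It is assumed equal throughout, then varied. Arm C is assumed to have no costs apart from those that accrue with NRU days.

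**Absolute difference.** Let W be the first-week cost, and H and M the hospital and home costs from day 7. Then (W + H) − (W + M) = H − M. The start point makes no difference.

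**Percentage saving.** From day 7 it is (H − M)/H. Over the whole course it is (H − M)/(W + H). The inflation is (W + H)/H, which is L/(L − 7) at equal daily cost. It does not depend on the size of the saving or on the home arm's expected time to recovery.

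| Stay L (days) | L/(L − 7) | 35% from day 7, over the whole course |
|---|---|---|
| 15 | 15/8 = 1.88 | 18.7% |
| 22.5 | 22.5/15.5 = 1.45 | 24.1% |
| 25 | 25/18 = 1.39 | 25.2% |
| 30 | 30/23 = 1.30 | 26.8% |

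If instead the 35% is a whole-course figure, costing from day 7 would show 0.35 × 22.5/15.5 = 50.8%.

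**Unequal daily cost.** If a first-week day costs r times a later day, the factor at L = 22.5 is (7r + 15.5)/15.5. That is 1.23 at r = 0.5 and 1.68 at r = 1.5.

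**Children per fixed budget.** With proportional saving s, a budget treats 1/(1 − s) times as many children.

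- From day 7, s = 0.35: 1/0.65 = 1.54.
- Whole course, s = 0.241: 1/0.759 = 1.32.
- Total children overstated: 1.538/1.318 = 1.17 times.
- Extra children overstated: 0.538/0.318 = about 1.7 times.

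Unlike the percentage, this overstatement depends on the saving. For extra children it is 1.50 times at a 10% day-7 saving and 1.90 times at 50%.

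**Average cost per recovered child.** At a 35% day-7 saving, home cost is 0.65 of hospital cost from day 7 and 0.76 over the whole course. If the proportion recovering at home, relative to hospital, lay between 0.65 and 0.76, the two windows would rank the programmes in opposite order. The protocol gives no expected recovery proportions, so this shows what is possible, not what is likely.

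**The case against.** The strongest defence is that the protocol gives its reason. Day 7 is where costs begin to differ, and leaving out a common cost is accepted practice for an incremental analysis. Incremental cost, incremental cost per unit of outcome and the difference in net benefit are all unchanged, and Hypothesis 2 could be tested on net benefit. This stands in full. A reader might infer that the day-7 start biases the comparison between arms. It does not.

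Second, Clinical Economics does not say whether results will be a difference, a ratio or a percentage, and the Rationale says only that more children could be treated, without a multiple. So the overstatement is conditional on what is reported. That also stands, but it does not dispose of the point. The one numerical cost target is a percentage, the resource claim is relative, and no other cost window is specified for either.

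Third, it is tempting to apply 1.45 to everything. It belongs to the percentage saving only, at equal daily cost and a 22.5-day stay. The early diet has more milk feeds than the later one, so daily costs may well differ.

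Fourth, the boundary is partly a choice: acute care before randomization is also common to all arms. Randomization is nevertheless the natural start, because it is where the compared regimens begin and where Data Analysis starts its outcome comparison.

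Finally, Data Analysis might be read as already placing the cost outcome over the whole course, leaving day 7 for the cost-benefit analysis alone. If so, the protocol has two cost windows and should say which serves which statement.

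**Conclusion.** The point holds for relative cost figures and not for the absolute difference. The day-7 start omits an NRU week that the home programme itself requires, and it does not match the enrolment start used for outcomes that include cost. Any percentage saving, benefit-cost ratio, cost per recovered child or children-per-budget statement built on it would err in favour of home care.

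The direction needs only a positive first-week cost and a home programme that is cheaper from day 7. The size rests on the stated stays and on unit costs that the protocol does not give: about 1.45 times for the percentage saving, within 1.30 to 1.88 across the stated stays and 1.23 to 1.68 across the assumed daily-cost ratios. At a 35% day-7 saving, total children per budget would be overstated about 1.17 times and extra children about 1.7 times.

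The documents do not support reading this as evidence that home care saves nothing: a real saving remains a saving under either start. Nor do they show that an inflated percentage is certain to be reported. The group size of 75 is not called into question, since it rests on weight gain.

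**What to change.** In Clinical Economics, count institutional and parental costs from randomization in all three arms, including the first NRU week, up to oedema-free weight-for-height above 80%. Base every percentage reduction, benefit-cost ratio, cost per recovered child and same-resources statement on that total. Keep the costing from day 7 only for the absolute difference between arms, and label it so. In Sample Size, state the period to which the 35% reduction refers. Align the cost window with the one in Data Analysis.

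The cost is small. NRU day costs are needed for arm C in any case, and the parents' questions on food, wages, transport and help at home would cover one more week. The remaining drawback is a smaller percentage saving.
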